2.1 Primary objective(s)

The primary objective of the randomized treatment epoch and of the overall study is to demonstrate that canakinumab treatment at a dose of 150 mg (or 2 mg/kg in patient weighing ≤ 40 kg) s.c. every 4 weeks is superior to placebo in achieving a clinically meaningful reduction of disease activity defined as resolution of the index flare at Day 15 and no new disease flares over 16 weeks of treatment.

2.2 Secondary objectives

The secondary objectives of the study are:

- To evaluate the percentage of patients who achieve a Physician Global Assessment of Disease Activity (PGA) <2 (“minimal” or “none”) at Week 16
- To evaluate the percentage of patients with the serologic remission at Week 16 (defined as C-reactive protein [CRP] ≤ 10 mg/L)
- To evaluate the percentage of patients with normalized Serum Amyloid A (SAA) level at Week 16 (defined as SAA ≤ 10 mg/L)
- To evaluate the percentage of canakinumab responders in Epoch 2 who maintain a clinically meaningful response (absence of new flares) when switched to canakinumab every 8 weeks compared to placebo (Epoch 3)
- To evaluate the long-term safety and tolerability and immunogenicity of canakinumab
- To evaluate the pharmacokinetics/ pharmacodynamics of canakinumab

2.3 Exploratory objectives

The exploratory objectives of the study are:

- To explore the profile in CRP and SAA over time
- To explore the PGA and Patient/ Parent’s global assessment of disease activity (PPGA) profiles over time
- To explore the Physician’s Severity Assessment of Disease Signs and Symptoms over time
- To explore the percentage of patients with the serologic remission defined as normalized SAA level in all patients who remain on randomized treatment or require blinded rescue over time
- To explore the percentage of patients who require blinded escape from Days 8 to 28
- To explore the number and duration of fever episodes by mean of patient diaries over time

- To explore the time to first new flare in responders in Epoch 2 switched to canakinumab every 8 weeks compared to placebo (Epoch 3)
- To evaluate the number of flares by patient and by Epoch
- To explore the use of rescue medication over time
- To explore percentage of patients who are able to reduce their corticosteroid maintenance dose at the end of each study epoch
- To explore the improvement in renal function and/ or proteinuria in patients with impaired renal function (eGFR <89 mL/min/1.73 m²) and/ or proteinuria at Baseline
- To explore the effect of the canakinumab-induced change of disease activity levels on aspects of Health-related Quality of Life. The following questionnaires will be used:
 - Auto-Inflammatory Disease Activity Index (AIDAI)
 - SF-12 Health Survey (SF-12) *to be completed by patients ≥18 years of age at Baseline*
 - Child Health Questionnaire – Parent Form 50 (CHQ-PF50) *to be completed by patients >5 - <18 years of age at Baseline*
 - Sheehan Disability Scale version 3 (SDS v3)
- To explore the relationships between disease-associated genetic mutations and drug response
- To explore the safety and efficacy of canakinumab in the non-randomized group of Japanese crFMF patients with non-exon 10 mutations, or patients >28 days but <2 years old entering the study in the open-label arm of Epoch 2, and in the roll-over TRAPS patients previously participating in clinical study CACZ885D2203 and/or the subsequent Multiple Patient Program (MPP) treatment plan CACZ885D2207M entering the study directly in the open-label arm of Epoch 3

3 Investigational plan

3.1 Study design

Together with CAPS, the conditions of TRAPS, HIDS and crFMF are a well characterized subset within the broader family of auto-inflammatory diseases.

The rationale for an umbrella protocol enrolling patients with these 3 conditions is based upon their similarity with CAPS, and is additionally based on:

- The shared clinical features, pathophysiology, and translational evidence of the efficacy of IL-1 inhibition
- The availability of preliminary data on the efficacy and safety of canakinumab in the open-label proof of concept studies in the 3 target diseases
- The availability of safety data in patients with a spectrum of auto-inflammatory diseases (e.g. CAPS and SJIA).
- The ability to make use of the specialized, expert diagnosis/treatment centers, where pediatric and adult patients with these conditions are usually referred

This study consists of 3 cohorts (one cohort per condition: TRAPS, HIDS and crFMF), and 4 study epochs as illustrated in [Figure 3-1](#). The cohort details of the study design are shown in [Figure 3-2](#) and [Figure 3-3](#). In order to provide access to treatment, roll-over TRAPS patients previously participating in clinical study CACZ885D2203 and/or the subsequent Multiple Patient Program (MPP) treatment plan CACZ885D2207M will be allowed to enter the study in Epoch 3 and the Japanese crFMF patients with non-exon 10 mutations or patients >28 days but <2 years old will enter the study in the open-label arm of Epoch 2.

Each cohort will follow the same study design across the 4 epochs:

1. A screening epoch to assess patients' eligibility of up to 12 weeks duration (Epoch 1)
2. A randomized treatment epoch (Epoch 2) of 16 weeks which will provide efficacy and safety data in a double-blind placebo-controlled parallel-arm setting.

This randomized treatment epoch will include 2 possible escape options:

- a. Blinded escape from Day 8 to Day 28
- b. Open-label treatment from Day 29 to Day 112
3. A randomized withdrawal epoch (Epoch 3) of 24 weeks where Canakinumab responder patients will be re-randomized to canakinumab 150 mg q8w or Placebo
4. An open-label treatment epoch (Epoch 4) of 72 weeks to collect long-term safety data for canakinumab

The non-randomized patient group including Japanese crFMF patients with non-exon 10 mutations and patients >28 days but <2 years old will follow the following study design across the 4 epochs:

1. A screening epoch to assess patients' eligibility of up to 12 weeks duration (Epoch 1)
2. An open-label epoch of 16 weeks (Epoch 2)
3. An open-label epoch of 24 weeks (Epoch 3)
4. An open-label treatment epoch of 72 weeks to collect long-term safety data for canakinumab (Epoch 4)

[figure not shown]
Figure 3-1 Overall study design

Figure 3-2 **Cohort detail:**
Screening (Epoch 1) and randomized treatment Epoch 2

[figure not shown]
[figure not shown]

Figure 3-3 **Cohort detail:**
Randomized withdrawal Epoch 3 and open-label treatment Epoch 4

3.1.1 Screening epoch (Epoch 1)

A screening epoch of up to 12 weeks will be used to assess the eligibility (flare frequency/disease activity periodicity) to one of the three study cohorts, allow patients to achieve significant biologic washout and to taper off non-allowed medications and/ or to achieve a stable regime with the permitted bridging therapies.

Patients will be asked to come fasting for screening and all subsequent visits.

At screening, the investigator will assign a patient to the respective cohort (i.e., TRAPS, HIDS or crFMF), or to the non-randomized groups, and will enter the respective condition into the IRT (Interactive Response Technology). Patients will receive a symptom diary and will be instructed to complete it and contact the site upon the first signs of a disease flare.

Patients who meet all eligibility criteria and who will show a flare during the screening epoch (Epoch 1) will be eligible to enter the randomized treatment epoch (Epoch 2). The date of onset of the flare which will result in randomization (index flare) will be entered on the eCRF.

Patients can be re-screened only once and no study-related re-screening procedure should be performed prior to written re-consent by the subject.

Mis-randomized patients are defined as cases where IRT randomization was performed by the site either prematurely or inappropriately prior to confirmation of the patient's final randomization eligibility and no study medication was administered to the patient. Mis-randomized patients will not be re-screened.

3.1.2 Randomized treatment epoch (Epoch 2)

3.1.2.1 Randomization

At baseline, eligible patients will be randomized in a ratio of 1:1 within each cohort to one of below 2 treatment arms:

- Canakinumab 150 mg (or 2 mg/kg for patients weighing ≤ 40 kg) every 4 weeks (q4w)
- Placebo

Patients from the non-randomized group will enroll to the open label arm of canakinumab 150 mg (or 2 mg/kg for patients weighing ≤ 40 kg) every 4 weeks (q4w). They will be eligible for add-on injection and up-titration as described in the following sections but always receive open label medication.

All patients will receive the first subcutaneous injection at Baseline and will return to the site every 4 weeks to receive additional injections of investigational treatment for 16 weeks.

The resolution of the index flare will be assessed at Day 15. Resolution of the index flare is defined as PGA <2 (“minimal” or “none”), **and** CRP within normal range (≤ 10 mg/L) or reduction by at least 70% from baseline. Patients whose index flare has resolved will not be up-titrated. If their index flare has not resolved by Day 15, they will be eligible for blinded escape (see [Section 3.1.2.2](#)).

Visits to assess efficacy and safety are scheduled at Day 15, Day 29 and subsequently at 4 weeks intervals during the randomized treatment epoch. Patients might receive an up-titration if they have persistent disease activity or they re-flare before Day 29 (see [Section 3.1.2.2](#)) or after Day 29 (see [Section 3.1.2.3](#)).

3.1.2.2 Blinded escape (non-resolution/ early re-flare before Day 29)

The assignment to blinded escape will be managed by the IRT.

Patients whose index flare has not resolved by Day 15 will be eligible for blinded escape.

If patients experience persistent “mild”, “moderate” or “severe” disease activity (i.e., PGA ≥ 2 [clinical flare]), or CRP persistent >10 mg/L with less than 40% reduction from baseline from Day 8 to Day 14, they will also be eligible for blinded escape at an unscheduled visit.

In case one of the conditions described above occurs, patients will receive a single add-on s.c. injection of canakinumab (150 mg s.c. [or 2 mg/kg for patients ≤ 40 kg]) from Day 8 to Day 28 but will not be unblinded to their randomized treatment (see [Table 3-1](#)). This will lead to blinded up-titration to the next dosing regimen according to the initial randomized treatment and will be initiated from Day 29 onward through IRT.

- Patients randomized to canakinumab 150 mg q4w will receive 2 injections of canakinumab on Days 29, 57 and 85 equaling to a canakinumab 300 mg q4w regimen
- Patients randomized to placebo will receive 1 injection of canakinumab and 1 injection of placebo each on Days 29, 57 and 85 equaling to a canakinumab 150 mg q4w regimen

If the patient’s condition is not improving after add-on injection, rescue medication should be used from Day 15 until treatment is administered at Day 29. All patients on blinded escape will be followed-up for efficacy and safety.

Non-randomized cohort

Canakinumab naïve Japanese crFMF patients with non-exon 10 mutations or patients >28 days but <2 years old will initiate open-label treatment receiving canakinumab 150 mg (or 2 mg/kg for patients weighing ≤ 40 kg) q4w at Day 1. Index flare resolution will be assessed at Day 15.

Patients experiencing persistent “mild”, “moderate” or “severe” disease activity (i.e., PGA ≥ 2 [clinical flare]), or CRP persistent >10 mg/L with less than 40% reduction from baseline from Day 8 to Day 28 can receive a single add-on s.c. injection of canakinumab (150 mg s.c. [or 2 mg/kg for patients ≤ 40 kg]). If the patient’s condition is not improving after add-on injection, rescue medication should be used until the patient’s next visit at Day 29 when study treatment will be administered.

In case of add-on injection, up-titration to canakinumab of 300 mg (or 4 mg/ kg for patients weighing ≤ 40 kg) q4w will be initiated from Day 29 onward through IRT. Those patients will not be eligible for any further up-titration but may stay in the study receiving canakinumab of 300 mg (or 4 mg/ kg for patients weighing ≤ 40 kg) q4w if they are considered partial responders by the investigator.

All patients in open label arm will be followed-up for efficacy and safety.

3.1.2.3 Open label treatment arm (re-flare on/ after Day 29)

If on Day 29 or after Day 29, patients still have “mild”, “moderate” or “severe” disease activity (PGA ≥ 2 [clinical flare] and CRP ≥ 30 mg/L [serological flare]), up-titration to the next dosing regimen is allowed and patients will initiate open label escape at the next scheduled visit including Day 29 (see [Table 3-1](#)).

The following up-titration will be initiated at the next scheduled visit based on the IRT information:

- Patients randomized to placebo will receive canakinumab 150 mg q4w. If they still have “mild”, “moderate” or “severe” disease activity (PGA ≥ 2 [clinical flare] and CRP ≥ 30 mg/L [serological flare]) or re-flare at the next scheduled visit, they will increase the dose to canakinumab 300 mg q4w
- Patients randomized to canakinumab 150 mg q4w will increase the dose to canakinumab 300 mg (or 4 mg/ kg for patients weighing ≤ 40 kg) q4w

Table 3-1 Criteria for add-on injection or up-titration in Epoch 2

	PGA criteria	CRP criteria	Treatment option	IRT update
Day 8 to 14	Persistent PGA ≥ 2 OR	CRP persistent >10 mg/L with less than 40% reduction from baseline	Add-on injection allowed	Blinded up-titration effective at next scheduled visit (Day 29)
Day 15	PGA ≥ 2 OR	CRP >10 mg/L and no reduction by at least 70% from baseline	No Index flare resolution* Add-on injection allowed (only if add-on injection was not received earlier)	Blinded up-titration effective at next scheduled visit
Day 16 to 28	PGA ≥ 2 OR	CRP >10 mg/L and no reduction by at least 70% from baseline	Add-on injection allowed (only if add-on injection was not received earlier)	Blinded up-titration effective at next scheduled visit
Day 29 to 112	PGA ≥ 2 AND	CRP ≥ 30 mg/L	Up-titration allowed	Open label up-titration effective at next scheduled visit including Day 29 visit

* For patient with index flare resolution at Day 15, criteria defined for Day 29 will be applied

Single Add-on injection is allowed only once in Epoch 2

For patients who already received blinded escape prior to Day 29 and require a second up-titration:

- Patients randomized to placebo *who received blinded escape* (150 mg q4w) *prior to Day 29* will receive open-label canakinumab 300 mg q4w
- Patients randomized to canakinumab 150 mg q4w *who received blinded escape* (add on 150 mg q4w) *prior to Day 29* must not further up-titrate

Patients who are on the highest allowed dose of canakinumab of 300 mg (or 4 mg/ kg for patients weighing ≤ 40 kg) q4w and re-flare (PGA ≥ 2 **and** CRP ≥ 30 mg/L) will not be eligible for any further up-titration but may stay in the study receiving canakinumab of 300 mg (or 4 mg/ kg for patients weighing ≤ 40 kg) q4w if they are considered partial responders by the investigator. If these patients discontinue treatment with canakinumab, they should remain in the study for safety follow-up.

All patients on the open-label treatment arm will be followed-up for safety.

3.1.3 Randomized withdrawal epoch (Epoch 3)

3.1.3.1 Re-randomization

All patients randomized to placebo at baseline and completing the randomized treatment epoch (Epoch 2) without any re-flare will be considered placebo-responders. To avoid exposure to canakinumab which may not be justified in light of the clinical status, these patients will be withdrawn from the study treatment.

Patients who initiated blinded escape or entered the open-label treatment arm in the randomized treatment epoch (Epoch 2), non-randomized cohort patients and roll-over TRAPS patients will not be re-randomized and will enter the open-label treatment arm in Epoch 3; for patient management details refer to [Section 3.1.3.2](#).

All patients randomized to canakinumab 150 mg (or 2 mg/kg for patients weighing ≤ 40 kg) q4w at baseline and completing the randomized treatment epoch (Epoch 2) who did not require blinded escape or to enter the open-label treatment arm will be re-randomized in a ratio of 1:1 to:

- Canakinumab 150 mg (or 2 mg/kg for patients weighing ≤ 40 kg) q8w
- Placebo

Re-randomized patients will receive the first s.c. injection on Day 113 and will return to the site every 8 weeks to receive additional injections of investigational treatment for 24 weeks.

Visits to assess efficacy and safety are scheduled at 8 weeks intervals during the randomized withdrawal epoch (Epoch 3). Patients might receive an up-titration if they re-flare at unscheduled visits (see [Section 3.1.3.2](#)).

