Investigational drug	The drug whose properties are being tested in the study; this definition is consistent with US CFR 21 Section 312.3 and is synonymous with “investigational new drug” or “investigational medicinal product.”
Investigational treatment	All investigational drug(s) whose properties are being tested in the study as well as their associated treatment controls. This includes any placebos, any active controls, as well as approved drugs used outside of their indication/approved dosage or tested in a fixed combination. Investigational treatment generally does not include protocol-specified concomitant background therapies when these are standard treatments in that indication.
Medication number	A unique identifier on the label of each investigational/study drug package in studies that dispense medication using an IRT system.
Protocol	A written account of all the procedures to be followed in a trial, which describes all the administrative, documentation, analytical and clinical processes used in the trial.

Premature subject withdrawal	Point/time when the patient exits from the study prior to the planned completion of all study treatment administration and/or assessments; at this time all study treatment administration is discontinued and no further assessments are planned, unless the patient will be followed for progression and/or survival.
Randomization number	A unique identifier assigned to each randomized patient, corresponding to a specific treatment arm assignment
Study drug/ treatment	Any single drug or combination of drugs administered to the patient as part of the required study procedures; includes investigational drug (s), active drug run-ins or background therapy.
Study/investigational treatment discontinuation	Point/time when patient permanently stops taking study/investigational treatment for any reason; may or may not also be the point/time of premature patient withdrawal.
Subject Number	A number assigned to each patient who enrolls into the study
Up-titration	If patient's condition requires dose increase, up-titration will be allowed through IRT at scheduled visits from Day 29 onwards. Up-titration is done stepwise until the maximum dose of canakinumab 300 mg q4w is reached.
Variable	A measured value or assessed response that is determined in specific assessments and used in data analysis to evaluate the drug being tested in the study

Amendment 1

Amendment rationale

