1.1 Statistical and analytical plans

The planned analysis is described in Section 9 (Data Analysis) of the study protocol which is available in Appendix 16.1.1 of the CSR.

This document covers statistical and analytical plans for the primary endpoint analysis i.e. the resolution of the index flare at the time of randomization and the absence of incident flares over the first 16 weeks after randomization, at Week 16 interim analysis but also covers the analyses for the Week 40 interim analysis and the final analysis after database lock. The data collected in this study up to the time of the Week 16 interim analysis will be part of the marketing authorization submission package of the ACZ885N project. All data collected up to Week 16 will be analyzed in the Week 16 interim analysis.

This study consists of 3 cohorts (one cohort per condition: TNF-receptor Associated Periodic Syndrome (TRAPS), Hyper IgD Syndrome (HIDS) and colchicine resistant Familial Mediterranean Fever (crFMF)), and 4 study epochs.

Each cohort will follow the same study design across the 4 epochs:

- A screening epoch to assess patients' eligibility of up to 12 weeks duration (Epoch 1)
- A randomized treatment epoch (Epoch 2) of 16 weeks which will provide efficacy and safety data in a double-blind placebo-controlled parallel-arm setting. This randomized treatment epoch will include 2 possible escape options: Blinded escape (from Day 8 to Day 28), Open-label treatment (from Day 29 to Day 112)
- A randomized withdrawal epoch (Epoch 3) of 24 weeks where Canakinumab responder patients will be re-randomized to canakinumab 150 mg q8w or Placebo
- An open-label treatment epoch (Epoch 4) of 72 weeks to collect long-term safety data for canakinumab.

In order to provide access to treatment, roll-over TRAPS patients previously participating in clinical study CACZ885D2203 and/or the subsequent Multiple Patient Program (MPP) treatment plan CACZ885D2207M will be allowed to enter the study in randomized withdrawal epoch (Epoch 3) and the Japanese crFMF patients with non-exon 10 mutations or patients >28 days but <2 years old (with bodyweight ≥ 3.75 kg) will enter the study in the open-label arm of randomized treatment epoch (Epoch 2). The non-randomized patient group including Japanese crFMF patients with non-exon 10 mutations and patients >28 days but <2 years old will follow the following study design across the 4 epochs:

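### Section 3.1.3.1 selects canakinumab patients for re-randomization by absence of escape, not by response, so a patient first found flaring on Day 113 can meet the written rule and be assigned to placebo

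*Protocol*

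**What the plan says.** Protocol 3.1.3.1 applies two different tests. For placebo patients the test is flare status: "All patients randomized to placebo at baseline and completing the randomized treatment epoch (Epoch 2) without any re-flare will be considered placebo-responders". For canakinumab patients it is absence of escape: those who complete Epoch 2 and "who did not require blinded escape or to enter the open-label treatment arm will be re-randomized in a ratio of 1:1". Protocol 3.1.3.2 likewise defines non-responders by whether they used blinded escape or entered the open-label arm.

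Elsewhere the intended population is responders. Protocol 3.1 describes Epoch 3 as the epoch "where Canakinumab responder patients will be re-randomized to canakinumab 150 mg q8w or Placebo". Protocol 2.2 and 5.2, the H5 text in Protocol 9.5.1, and SAP 1.2 and 1.10.2.1 say the same.

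On timing, Protocol 3.1 gives "Open-label treatment from Day 29 to Day 112", SAP 1.1 repeats it ("Open-label treatment (from Day 29 to Day 112"), and the last row of Table 3-1 also stops at Day 112. Protocol 9.6 names Day 113 as the final Epoch 2 visit, and SAP Table 2-1 places it in Epoch 2. But "Re-randomized patients will receive the first s.c. injection on Day 113", and the dosing example in SAP 1.3 counts that injection in Epoch 3.

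Other text sets no last day. The Glossary says "up-titration will be allowed through IRT at scheduled visits from Day 29 onwards". The running text of 3.1.2.3, the up-titration paragraph of 5.3 and footnote 6 of Table 6-1 are similarly open-ended.

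**The concern.** Absence of escape can stand in for response only if every Epoch 2 flare can lead to escape before re-randomization. A flare first seen on Day 113 cannot, if escape closes on Day 112. That patient is a non-responder on the primary endpoint but has not escaped, and the rule as written admits the patient to a 1:1 randomization that includes placebo.

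What is at stake is mainly patient care: a patient in active flare could be assigned to placebo at the visit where the flare is recorded. Scheduled Epoch 3 visits are 8 weeks apart under 3.1.3.1, so earlier relief would depend on an unscheduled visit or on rescue medication. There is also a small analysis inconsistency. SAP 1.10.5 analyses time to first flare in all re-randomized patients, whereas the objective in Protocol 2.3 refers to responders.

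**Working it through.** **Calendar.** Day 1 plus 16 weeks is 1 + 16 × 7 = Day 113, and Day 113 plus 24 weeks is 113 + 24 × 7 = Day 281. Both match the plan's epoch boundaries. The scheduled visits after Day 15 (Table 6-1) are Days 29, 57, 85 and 113. Days 29, 57 and 85 lie inside the Day 29–112 escape window; Day 113 lies outside it.

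**The patient.** Take a canakinumab patient whose index flare resolved at Day 15, who never escaped, and who on Day 113 has PGA ≥2 and CRP ≥30 mg/L for the first time.

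- *Primary endpoint (Protocol 9.4.1):* non-responder, because a new flare occurred within the 16 weeks.
- *Table 3-1, Protocol 3.1, SAP 1.1:* escape is no longer open on Day 113.
- *3.1.3.1 taken literally:* Epoch 2 completed and no escape, so re-randomized. The paragraph listing who is not re-randomized covers only escaped, non-randomized and roll-over patients.
- *3.1.3.2:* not a non-responder as defined there, because that definition rests on escape.
- *Glossary, 3.1.2.3 text, 5.3, Table 6-1 footnote 6:* up-titration has no end day, so the patient can be said to require open-label treatment and is not re-randomized.
- *3.1 and 5.2:* only responders are re-randomized, so this patient should not be. However, 5.2 refers to 3.1.3 for the details.

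The plan therefore gives two answers for one patient and no rule on which prevails.

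**Size per affected patient.** Under 1:1 allocation the chance of placebo is 1/2 if the literal rule is applied, and 0 if response through Day 113 is required.

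**Frequency.** The documents give no rate, so the following is assumption only. Let m be the number re-randomized in a cohort (at most 30, Protocol Section 4) and f the share of them first flaring on Day 113. The expected number of flaring patients on placebo is m × f / 2, and the chance of at least one is 1 − (1 − f/2)^m.

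- m = 10, f = 2%: 10 × 0.02 / 2 = 0.1 patients; 1 − 0.99^10 = about 10%.
- m = 30, f = 10%: 30 × 0.10 / 2 = 1.5 patients; 1 − 0.95^30 = about 79%.

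This range shows only that the event could be rare or likely within a cohort. It does not estimate the risk.

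**Effect on analyses.** H5 is limited to Epoch 2 responders who were re-randomized (Protocol 9.5.1, SAP 1.10.2.1). The Day 113 flarer is outside H5 under the current wording, and also outside it if never re-randomized, so the H5 population is the same either way. The primary endpoint is settled before re-randomization. Only the exploratory time-to-first-flare analysis would take in such a patient.

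**The case against.** The best defence is that the intent is clear and a check already exists. Protocol 3.1 and 5.2 say responders. Section 5.3 has the site confirm that the patient qualifies before contacting the IRT. The phrase used in 3.1.3.1 is a test of need, and a patient flaring on Day 113 arguably needs open-label treatment. Up-titration takes effect at the next scheduled visit, so a flare found between Days 86 and 112 is already acted on at Day 113. Figures 3-2 and 3-3, some Table 6-1 rows and the body of Table 6-2 cannot be seen and might settle the flow.

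Much of this stands: it shows what was meant and makes the open-label reading reasonable. It does not remove the conflict. Section 5.3 does not define what qualifies a patient, 5.2 sends the reader back to 3.1.3, and 3.1.3.2 defines non-response by escape.

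The consequences are also softened: "Patients might receive an up-titration if they re-flare at unscheduled visits", and rescue medication is permitted under 5.5.6.

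Three stronger inferences should be resisted.

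- A reader might infer that H5 is biased or loses patients through this wording. It does not, as the working shows.
- A reader might count assignment to q8w as a harm of this gap. But 3.1.3.2 also moves non-responders in the open-label arm to q8w, so only the placebo assignment is specific.
- A reader might take 150 mg q4w as the most that a re-randomized patient could later receive. That is only the step named in 3.1.3.2; the Glossary allows stepwise up-titration to 300 mg q4w.

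**Conclusion.** The point holds as an internal conflict with a patient-safety consequence. The documents do not support reading it as a deliberate choice to randomize flaring patients to placebo, because the responder wording shows the opposite intent. Under the literal rule, a canakinumab patient first found flaring on Day 113 has a 1 in 2 chance of placebo. How many such patients there would be cannot be taken from the documents. The primary endpoint and H5 stand as planned; the only analysis touched is exploratory. The conclusion rests on the visible text, and the missing figures and schedule rows could narrow it. It deserves correction because the rule governs allocation at the visit itself, where SAP text cannot help.

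**What to change.** 1. In 3.1.3.1 and the IRT, re-randomize a canakinumab patient only if the index flare resolved at Day 15, no escape was used, and no new flare occurred through Day 113 inclusive. The Day 113 PGA and local CRP must be known first. The Day 15 condition also covers a patient with an unresolved index flare who received no add-on injection, which Table 3-1 describes as allowed.
2. Change Day 112 to Day 113 in Protocol 3.1, Table 3-1 and SAP 1.1, so that a Day 113 flare triggers open-label up-titration.
3. Add patients who fail the check to the non-responders in 3.1.3.2, send them to the Epoch 3 open-label arm, and state the dose. For a Day 113 flare this is 300 mg (or 4 mg/kg at 40 kg or less), the next step under 3.1.2.3, with the interval rules of 3.1.3.2.
4. In SAP 1.10.5, limit time to first flare to re-randomized Epoch 2 responders.

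The cost is a few wording changes, one IRT check and one SAP sentence. PGA and CRP at this visit are already needed for H2 and H3. Re-randomization would have to wait for the local CRP, which by 6.4.1 becomes available only after the PGA is done, and slightly fewer patients would be re-randomized.
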